Comparison of Buffered vs. Non-Buffered Lidocaine used in Dental and Oral Surgical Procedures: Clinical Outcomes

NCT number NCT02620683
Document Date 10/30/2015
**Most recent IRB approval Date
(for this document version)** 07/10/2017

RESEARCH PROTOCOL

Comparison of Buffered vs. Non-Buffered Lidocaine used in dental and oral surgical procedures: Clinical Outcomes

PI Dr [name].

Co-PI Dr [name], Dr [name]

Goal:

Assess the clinical impact of buffered lidocaine with epinephrine as compared to the non-buffered drug combination used in dental and oral surgical procedures.

Background:

Based on discovery of the anesthetic effects and the invention of the hypodermic syringe at the end of the 19th century, cocaine was rapidly adopted as a means of blocking painful sensory impulses during surgical procedures.(1) The discovery of procaine early in the 20th century led to this newer drug replacing cocaine avoiding the potential addictive properties of the latter. Lidocaine and its derivatives, products of the late 20th century, mepivacaine, bupivacaine, and articaine, are widely used today with invasive procedures.(2) Recently local anesthetics have been administered in vehicles such as liposomes to produce longer term sensory nerve blockade, reducing the need for analgesic drugs, chiefly opioids, to reduce pain.(3)

The addition of a vasopressor, usually epinephrine, to lidocaine and other injected local anesthetics serves to prolong the anesthetic effect by reducing blood flow to the anatomic area and the diffusion of the drug away from the anatomic site of injection. To prolong the shelf life of the vasopressor, the drug combination must be formulated with a low pH, approximately pH 3.5 for lidocaine with 1/100k epinephrine. When injected, the low pH causes the “sting” felt by patients on injection.

Perhaps more important, the local anesthetic drug is more effective both in onset and potency if the pH is closer to the drugs pKa, over 8.0. The drug injected at a neutral pH reduces the need for buffering by tissue fluid while retaining the desired qualities of the vasopressor.

Until recently, buffering the drug combination with bicarbonate just prior to injection was impractical for the small quantities used in intraoral procedures. However, today we do have a kit capable of efficiently accomplishing this end.(Anutra Medical, NC)

Mean maximum blood levels of non-buffered local anesthetic drugs occurs approximately 30min post oral injection.(4) No data exist on peak blood levels for buffered local anesthetics used in dental and oral surgical procedures

Rationale:

Anecdotal reports suggest buffering lidocaine with epinephrine just before intraoral injection reduces time of onset, results in a deeper anesthetic effect, without the “sting” with injection from a low pH. Additional data are needed to establish clinical important outcomes such as the peak blood level of lidocaine as compared to the non-buffered drug combination.

Clinical pilot studies are proposed as the start of a series of investigations to support or modify the use of the buffered anesthetic for intraoral procedures.

Specific Aims:

Compare blood levels at 30min post injection mandibular block with buffered and non-buffered 2% lidocaine with 1/100k epinephrine.

Assess outcomes (pain levels during and post-injection, and onset of anesthesia symptoms) after buffered and non-buffered oral administration of 2% lidocaine with 1/100k epinephrine.

Assess possible topical anesthetic properties of buffered and non-buffered oral administration of 2% lidocaine with 1/100k epinephrine

Hypotheses:

No difference in peak blood levels exist between buffered and non-buffered intraoral injection of 2% lidocaine with 1/100k epinephrine.

Injection of buffered local anesthetic will produce less discomfort for the subject as compared to the drug with a low pH.

Buffered local anesthetic will not produce a topical anesthetic effect

Study Time Frame: 6 months

Month One

IRB approvals. Recruit dental student volunteers. Prepare case-books.

Months Two-Three

Clinical Study

Months Four-Five

Analyze Lab, QOL data

Month Six

Prepare Abstracts, Papers

Methods: Blinded, Randomized Clinical Design

Recruit subjects with IRB approved consent at UNC

Target enrollment 24 subjects

Subjects will serve as their own controls in a cross-over study design.

Sample size justification: Primary interest is estimation of effect size from pilot study.

24 subjects should be sufficient to provide data to assess whether a larger study is warranted and provide estimates for sample size calculation for larger studies.

Vital signs recorded: 10 min before, during at 30min intervals and after post-anesthetic clinical signs disappear: targeted lower lip no longer numb.

Randomized subjects to be injected alternatively with 4cc of buffered and

4cc non-buffered oral administration of 2% lidocaine with 1/100k epinephrine.

SAS will be used to create randomization schedules:

The randomization will be performed first to type of drug given with a balanced randomization (half subjects buffered; half to non-buffered)

An OMS resident, [name], will administer the drugs in the OMS clinic.

In week One each subject would receive anesthetic to block the inferior alveolar and lingual N; Halstead or Gow-Gates techniques. No Buccal N. block.

At least a week later injections would involve the alternate local anesthetic combination.

Venous blood samples would be drawn from the antecubital fossa 30min post oral injection and assayed for blood lidocaine levels

Timed Assessment: pre, during injection, and post-anesthetic for Clinical

Onset of Anesthesia Signs: subject reported molar area numbness and numb lower lip on ipsilateral injected side.

Assessment for pain level on injection; modified Likert-type scale

In addition at each clinic session an assessment of a topical anesthetic effect on contralateral lower lip with 5 drops of the injected drug placed on the clinically dry lower lip mucosa, Outcome yes/no.

Study Subjects:

Inclusion Criteria

Age 20-35 years

ASA I

Willingness to complete QOL instrument

Willingness to participate in two sessions

Exclusion Criteria

Allergy to lidocaine class of anesthetic drugs

Local anesthetic drug use in past week

Current symptoms teeth or oral mucosa

Data Collection: UNC OMS clinic

Venous blood samples (10cc) will be drawn from the antecubital fossa 30min post oral injection.. [name], RN OMS clinic

Timed assessment pre, during injection, and post-anesthetic clinical

Signs: molar area anesthesia, incisor area anesthesia, and numb lower lip for topical

Data Collection/Analysis:

Data will be managed by [name] staff. Data collection forms and questionnaires for clinical data will be developed to use Teleform for direct scanning input into an ACCESS database. Similar forms have been used in previous studies. All databases are stored on a password protected server with specific group assignment. SAS will be used for database management and statistical analysis. Descriptive statistics are used to verify correct entry through range and logical checks.

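### Hypothesis 1 concerns peak blood lidocaine, but blood is drawn only at 30 min, so the trial can conclude about the 30-min level and not the peak

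*Combined protocol and SAP*

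**What the plan says.** The Hypotheses section states "No difference in peak blood levels exist between buffered and non-buffered intraoral injection". Specific Aim 1 is narrower: "Compare blood levels at 30min post injection mandibular block with buffered and non-buffered 2% lidocaine with 1/100k epinephrine". Methods gives the draw as "Venous blood samples would be drawn from the antecubital fossa 30min post oral injection and assayed for blood lidocaine levels", and Data Collection repeats it: "Venous blood samples (10cc) will be drawn from the antecubital fossa 30min post oral injection". No other blood-draw time appears; the half-hourly intervals in Methods are for vital signs.

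The basis for 30 min is in the Background: "Mean maximum blood levels of non-buffered local anesthetic drugs occurs approximately 30min post oral injection". The next sentence there is "No data exist on peak blood levels for buffered local anesthetics used in dental and oral surgical procedures".

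The sample size justification says "Primary interest is estimation of effect size from pilot study" and expects the data to "provide estimates for sample size calculation for larger studies". The Statistical analysis section defines no maximum concentration and no time to peak, and has no step that derives a peak from one sample.

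**The concern.** The hypothesis names a quantity that the trial neither measures nor derives. With one sample per session, a 30-min level equals the peak only if the peak falls at 30 min. A comparison of peaks needs that to hold, at least roughly, for both solutions. The document supports it for one and says it has no data for the other.

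If the two solutions peak at different times, the 30-min difference can be smaller or larger than the peak difference. A result of no difference reported under Hypothesis 1 would then be a statement about peaks that the data cannot support, because a difference before or after 30 min would go unseen. The Rationale names peak level among the outcomes that need data, so a reader could take the 30-min result as filling that gap. The effect size could also be carried into the planning of a larger study as a peak effect, although the document does not say which outcome later studies would use.

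**Working it through.** **Side-by-side reading**

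| Place | Quantity or time |
|---|---|
| Hypotheses, first hypothesis | peak level |
| Specific Aims, first aim | level at 30 min |
| Methods, blood sampling | 30 min only |
| Data Collection, blood sampling | 30 min only |
| Background, non-buffered drug | mean peak at about 30 min |
| Background, buffered drug | no peak data |
| Statistical analysis | no derived peak |

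The aim and the sampling time agree with each other. Only Hypothesis 1 departs from them. The plural in the sampling statements fits many subjects and two sessions, and does not imply several time points. The plan gives no power, effect size or SD for blood level, so there is no stated figure to reproduce.

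**Illustration of size (not an estimate)**

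Assumptions, none of them in the documents: a one-compartment model with first-order absorption, the same half-life for both solutions (60, 90 or 120 min), a non-buffered peak at exactly 30 min, and a range of buffered peak times.

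- C(t) = dose × ka/(ka − ke) × [exp(−ke·t) − exp(−ka·t)]
- ke = ln 2 / half-life
- ka is solved from tmax = ln(ka/ke)/(ka − ke)

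*One case in full: half-life 60 min, buffered peak at 20 min, equal doses.* ke = 0.6931/60 = 0.01155 per min. For tmax = 20, ka = 0.1342; per unit dose the peak is 0.7937 and the 30-min level is 0.7542, so the share of own peak seen at 30 min is 0.7542/0.7937 = 95.0%. For the non-buffered curve, tmax = 30 gives ka = 0.0730 and a peak of 0.7071. The ratio of peaks is 0.7937/0.7071 = 1.122; the ratio at 30 min is 0.7542/0.7071 = 1.067. A true peak difference of 12% would be seen as 7%.

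*30-min level as a share of the solution's own peak (does not depend on dose):*

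| Peak time (min) | Half-life 60 | 90 | 120 |
|---|---|---|---|
| 10 | 82% | 87% | 90% |
| 15 | 88.9% | 92.0% | 93.7% |
| 20 | 95.0% | 96.3% | 97.0% |
| 25 | 98.8% | 99.1% | 99.2% |
| 35 | 99.1% | 99.2% | 99.3% |
| 45 | 93.6% | 94.3% | 94.9% |

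Across all three half-lives, the share is at least 95% for peaks between 20.0 and 42.9 min, and at least 90% for peaks between 15.8 and 50.1 min.

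*Buffered to non-buffered ratios, equal doses (half-life 60/90/120):*

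| Buffered peak (min) | Ratio of peaks | Ratio at 30 min | Gap (points) |
|---|---|---|---|
| 20 | 1.122/1.080/1.059 | 1.067/1.040/1.028 | −5.6/−4.0/−3.2 |
| 45 | 0.841/0.891/0.917 | 0.787/0.840/0.870 | −5.4/−5.1/−4.7 |
| 10 | 1.260/1.166/1.122 | 1.034/1.019/1.013 | −22.6/−14.7/−10.9 |

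An earlier buffered peak makes the 30-min contrast understate the difference; a later one makes it overstate the difference. Direction also depends on dose. If the buffered dose were half and its peak at 20 min, the ratio of peaks would be 0.561/0.540/0.530 and the ratio at 30 min 0.533/0.520/0.514: a true reduction of 44–47% would appear as 47–49%. That case is shown only because the Statistical analysis section describes a 1% versus 2% contrast while Methods describes 2% for both; which is meant is a separate matter.

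**Set against the pilot's precision**

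Assumed within-subject CV of 10, 20 or 30%, 24 subjects, paired analysis: half-width of the 95% CI = t(0.975, 23) × √2 × CV / √24 = 2.069 × 1.414 × CV / 4.899. This gives 6.0%, 11.9% and 17.9%.

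**The case against.** The strongest reply is that 30 min was chosen as a stand-in for the peak. The Background places the reason for it beside the caveat about the buffered drug, and Specific Aim 1 already names what is measured. An analyst following the aims would report a 30-min level, so this is one loose word in a pilot protocol. It could be cured by keeping the word peak and stating the assumption that both solutions peak near 30 min.

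Much of this stands. The sampling time is a reasonable choice, the aim is correctly worded, and nothing in the conduct of the trial changes. Stating the assumption would be better than leaving it unsaid. It would still leave Hypothesis 1 resting on something that the protocol has no data for and that this design cannot test.

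The numerical illustration is also open to criticism. The half-lives, buffered peak times and CVs are assumed, so the figures show that a distortion is possible, not that it is likely. The modest gaps belong to the 20- and 45-min examples; a 10-min peak gives 11 to 23 points, which need not lie within the pilot's imprecision. The half-width assumes a paired analysis, whereas the plan names a rank sum test. Finally, the reported faster onset of anesthesia is anecdotal, concerns numbness and not blood level, and is not evidence that the systemic peak shifts.

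**Conclusion.** The concern holds. As worded, Hypothesis 1 calls for a conclusion on peak levels from data that give only the 30-min level. This follows from the text alone and does not depend on the model.

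The consequence is one of interpretation, minor to moderate. Its numerical size cannot be taken from the documents. Under the assumed model it is about 1% of a solution's own peak for peaks at 25 to 35 min, and about 2 to 6 percentage points of the between-solution contrast in the 20- and 45-min examples (the half-dose case included). Distortions of 2 to 6 points would generally lie within a CI half-width of about 6 to 18%. They would be larger for a very early peak. Because the mismatch is systematic, more subjects in a later study sampled the same way would not remove it.

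**What to change.** Restate Hypothesis 1 in terms of venous lidocaine concentration 30 min after injection, so that it matches Specific Aim 1. Add a sentence that no conclusion about peak level or time to peak is drawn for either solution. Label any blood-level effect size passed to later studies as a 30-min effect. The Rationale's mention of peak level can stay as a description of the wider gap in knowledge.

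The cost is wording only, with no extra draw, subject or analysis. The price is a narrower claim: the 30-min level, not the peak.
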